5.6 Procedure for Breaking the Blind

Not applicable for this open-label trial.

5.7 Follow-up of Adverse Events

5.7.1 Follow-up of Nonserious Adverse Events

Nonserious AEs that are identified at any time during the trial must be recorded on the AE CRF with the current status (ongoing or resolved/recovered) noted. All nonserious events (excluding IREs) that are ongoing at the last scheduled contact will be recorded as ongoing on the CRF. For any AE having been identified throughout the trial, during data analysis, additional relevant medical history information may be requested by the sponsor to further ascertain causality (including, but not limited to, information such as risk-related behavior, family history and occupation). The follow-up information after the last scheduled contact will be recorded in the subject's medical record.

5.7.2 Follow-up of Serious Adverse Events and Immediately Reportable Events

This trial requires that subjects be actively monitored for SAEs and IREs until the last scheduled contact as specified in Section 3.7.6.

Serious AEs and IREs that are identified or ongoing at the last scheduled contact must be recorded on the AE CRF page. Any new information (eg, Resolved) related to the SAE or IRE obtained from the last scheduled contact of the subject until the last scheduled contact of the last subject in the entire trial must be reported to the sponsor with the IRE form and so on, and the information must be recorded on the AE CRF page. The investigator or subinvestigator must follow SAEs and IREs until the events have resolved or are stabilized, or the subject is lost to follow-up or has died, and report any significant follow-up information to the sponsor with the IRE form and so on. Resolution means the subject has returned to the baseline state of health and stabilized means that the investigator or subinvestigator does not expect any further improvement or worsening of the subject's condition.

5.7.3 Follow-up and Reporting of Serious Adverse Events and Immediately Reportable Events Occurring After Last Scheduled Contact

Any new SAEs or IREs reported to the investigator or subinvestigator, which occur after the last scheduled contact and are determined by the investigator or subinvestigator to be reasonably associated with the use of the IMP, should be reported to the sponsor. This may include SAEs or IREs that are captured on follow-up telephone contact or at any other time point after the defined trial period. The investigator or subinvestigator should follow SAEs or IREs identified after the last scheduled contact and continue to report any significant follow-up information to the sponsor with the IRE form and so on until the events have resolved or are stabilized, or the subject is lost to follow-up or has died.

6 Pharmacokinetic Analysis

6.1 Pharmacokinetic Methods

6.1.1 Primary Endpoints

C_{max} and AUC_t of brexpiprazole

6.1.2 Secondary Endpoints

- 1) Plasma concentration-time profiles of brexpiprazole
- 2) Brexpiprazole AUC $_{\infty}$, t_{max} , λ_z , AUC $_{\infty}$ Extrap, $t_{1/2,z}$, CL/F, CL/F/BW, and t_{last}

6.1.3 Datasets for Analysis

The bioequivalence analysis set is defined as the analysis dataset (see Section 7.2.1).

6.1.4 Analysis Methods

The PK parameters of brexpiprazole (C_{max} , AUC_t , AUC_∞ , t_{max} , $t_{1/2,z}$, λ_z , t_{last} , CL/F, CL/F/BW, AUC_{-} %Extrap) will be calculated through a noncompartmental PK analysis. The plasma concentrations and estimated PK parameters will be presented with descriptive statistics by formulation and administration method.

6.2 Pharmacodynamic Methods

No pharmacodynamic parameters will be evaluated for this trial.

6.3 Pharmacokinetic/Pharmacodynamic Methods

No pharmacokinetic or pharmacodynamic-related analyses are scheduled for this trial.

6.4 Pharmacogenomic Methods

No pharmacogenomic-related analyses are scheduled for this trial.

7 Statistical Analysis

The definition of analysis sets and analysis method by endpoint are summarized below. The analysis plan will be described in detail in the Statistical Analysis Plan separately. The Statistical Analysis Plan is to be determined before data lock.

7.1 Determination of Sample Size

Based on the BE Guideline, the sample size was calculated so that the 90% confidence intervals of geometric mean ratios for brexpiprazole C_{max} and AUC_t between ODT (with or without water) and conventional tablet would fall within the bioequivalence range of 0.8 to 1.25.

In a brexpiprazole 4-mg ODT BA study conducted in Japan (331-102-00019) and brexpiprazole bioequivalence studies conducted outside Japan (331-10-243 and 331-13-209), the within-subject variance for natural log-transformed C_{max} and AUC_t values was greatest for C_{max} in Trial 331-13-209 (at 0.035).

Assuming a geometric mean ratio of 1.0 for brexpiprazole C_{max} between ODT (with and without water) and conventional tablet, and a within-subject variance of 0.035 for natural log-transformed C_{max} , to achieve at least 90% power will require 6 subjects in each sequence, 18 in total. Considering the possibility of some subjects being excluded from analysis due to discontinuation, etc, the number of subjects was set as 7 for each sequence and 21 in total.

7.2 Datasets for Analysis

7.2.1 Bioequivalence Analysis Set

All subjects who provided C_{max} or AUC_t through Period 1, Period 2, and Period 3

7.2.2 Safety Population

All subjects who received at least one dose of IMP

7.3 Handling of Missing Data

There will be no imputation for missing data.

7.4 Primary Endpoint Analyses

The following analysis will be performed on the bioequivalence analysis set:

The C_{max} and AUC_t of brexpiprazole will be analyzed using the natural log-transformed values in a mixed effect model with sequence (1, 2, and 3), formulation and administration method (conventional tablet, ODT without water, ODT with water), and period (Period 1, Period 2, and Period 3) as fixed effects and the subjects within each sequence as a random effect. The 90% confidence intervals of geometric mean ratios for brexpiprazole C_{max} and AUC_t between ODT (with or without water) and conventional tablet will be calculated. If the 90% confidence intervals are within the range of 0.8 to 1.25, the 2 formulations and administration methods will be judged to be bioequivalent.

If an add-on subject study is conducted, bioequivalence will be assessed on the same basis from the result of combining the initial study and the add-on subject study by including study as a fixed effect in the above mixed effect model.

If there are any subjects who had no evaluable parameters through Period 1, Period 2, and Period 3, analysis in which those subjects are included will be performed.

The Kenward–Roger method will be used to estimate the degrees of freedom in the mixed effect model analysis.

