2.2 Dosing Rationale

2.2.1 Regimen

According to the Guideline for Bioequivalence Studies for Formulation Changes of Oral Solid Dosage Forms Q&A (Attachment 3),¹² a bioequivalence study conducted when applying for approval of dosage forms different from conventional tablets, from the characteristics of ODT formulation, should be basically conducted as a bioequivalence study of "conventional tablets administered with water" and "proposed formulation administered without water," and a bioequivalence study of "conventional tablets administered with water" and "proposed formulation administered with water," and therefore administration both with and without water was decided. In addition, according to the BE Guideline, ¹¹ study drugs should be taken, as a rule, with a certain amount of water, between 100 to 200 mL (typically 150 mL) after fasting for at least 10 hours, and it was therefore decided that the amount of water for administration of investigational medicinal products (IMPs) would be 150 mL.

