2.3 Trial Objectives

The purpose of the present trial is to investigate the bioequivalence of brexpiprazole ODT 2 mg and brexpiprazole conventional tablet 2 mg.

3 Trial Design

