7.7 Judgement for Conduct of Add-on Subject Study

If bioequivalence cannot be demonstrated in the initial study because of an insufficient number of subjects, an add-on subject study can be performed in accordance with this protocol.

The add-on subject study will be performed using not less than half the number of subjects in the initial study. No add-on subject study will be performed in the following cases:

- 1) If the results of the initial study show that the point estimates of the geometric mean ratios for AUC_t and C_{max} between ODT and conventional tablet do not fall within the range of 0.8 to 1.25, and
- 2) If the required number of subjects for the add-on subject study estimated from the results of the initial study is considered to be a sample size that is ethically or scientifically infeasible.

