10.1 Statistical Analyses of Primary Pharmacokinetic Endpoints

The following analysis will be performed on the bioequivalence analysis set:

The C_{max} and AUC_t of brexpiprazole will be analyzed using the natural log-transformed values in a mixed effect model with sequence (1, 2, and 3), formulation and administration method (conventional tablet, ODT without water, ODT with water), and period (Period 1, Period 2, and Period 3) as fixed effects and the subjects within each

sequence as a random effect. The Kenward–Roger method will be used to estimate the degrees of freedom in the mixed effect model analysis. The 90% confidence intervals of geometric mean ratios for brexpiprazole C_{\max} and AUC_t between ODT (with or without water) and conventional tablet will be calculated. If the 90% confidence intervals are within the range of 0.8 to 1.25, the 2 formulations and administration methods will be judged to be bioequivalent.

If an add-on subject study is conducted, bioequivalence will be assessed on the same basis from the result of combining the initial study and the add-on subject study by including study as a fixed effect in the above mixed effect model.

If there are any subjects who had no evaluable parameters through Period 1, Period 2, and Period 3, analysis in which those subjects are included will be performed.

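### Does the plan need a written rule for the case where one ODT comparison passes and the other fails?

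*Protocol*

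**What the plan says.** Protocol 2.3 poses one question: "The purpose of the present trial is to investigate the bioequivalence of brexpiprazole ODT 2 mg and brexpiprazole conventional tablet 2 mg". Section 2.2.1 explains why there are two ODT arms. The guidance it cites asks for a comparison with the tablet without water and another with water, "and therefore administration both with and without water was decided".

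Protocol 7.4 calculates Cmax and AUCt intervals for the ODT, with or without water, against the tablet. It then applies the sentence ending "within the range of 0.8 to 1.25, the 2 formulations and administration methods will be judged to be bioequivalent"; SAP 10.1 repeats it. Combined data after an add-on are to be assessed on the same basis.

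Protocol 7.7 (repeated in SAP 4.1) sets the trigger: "If bioequivalence cannot be demonstrated in the initial study because of an insufficient number of subjects, an add-on subject study can be performed". The first case ruling out an add-on concerns point estimates "between ODT and conventional tablet do not fall within the range of 0.8 to 1.25", and does not separate the two ways of taking the ODT.

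On sample size, Protocol 7.1 states that, at a ratio of 1.0 and a variance of 0.035, "to achieve at least 90% power will require 6 subjects in each sequence, 18 in total". Enrolment is 21.

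**The concern.** There are two comparisons and one decision sentence. The sentence can be read as a verdict for each pair or as a requirement on all the intervals together, and no text covers a split. The add-on trigger speaks of bioequivalence as one thing, so it is unclear whether a single failed comparison counts.

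The gap falls where the add-on rule operates. That rule matters only after the initial study fails, and under the planning assumptions most failures are splits. If the reading were chosen with the results known, it could decide whether the ODT is declared equivalent and whether at least 11 more healthy men are dosed (half of 21 is 10.5). The stated 90% power might also be taken as power for both comparisons, which 18 subjects do not quite give.

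**Working it through.** **Inputs.** From Protocol 7.1: true ratio 1.0 for both comparisons, within-subject variance 0.035 for ln Cmax, 18 evaluable and 21 enrolled, limits 0.8 to 1.25 (±0.2231 on the log scale). From 7.4: 90% intervals, that is, two one-sided tests at 5%. For complete data from the 3×3 crossover, the residual degrees of freedom are 2n − 4. The two contrasts share the tablet arm: each has variance 2σ²/n and their covariance is σ²/n, so their correlation is 0.5.

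**The plan's own figure, one comparison.** SE = √(2 × 0.035 / n).

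- n = 18: SE = 0.0624, t(0.95; 32 df) = 1.694, half-width about 0.106. Then (0.2231 − 0.1056) / 0.0624 = 1.88, and 2Φ(1.88) − 1 ≈ 94%. Integrating over the estimated variance gives 93.7%.
- n = 21: SE = 0.0577, and the integrated power is 96.8%.
- n = 15: 87.5%.

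The smallest multiple of three reaching 90% is 18, so the stated number is reproduced. It is the number for one comparison.

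**Both comparisons, Cmax (simulation, 2,000,000 trials).** The chance of exactly one pass is 2 × (power for one − power for both).

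| Evaluable | One comparison | Both pass | Exactly one | Neither | Splits among failures |
|---|---|---|---|---|---|
| 18 | 93.65% | 88.70% | 9.9% | 1.4% | 88% |
| 21 | 96.84% | 94.21% | 5.3% | 0.5% | 91% |

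AUCt barely matters. The without-water AUCt interval from study 331-102-00019 (0.9549 to 1.0575) implies a variance of about 0.008, assuming 17 subjects and 30 df. Including it leaves the shares at 88% and 91%. If AUCt were as variable as Cmax (0.035, correlation between the two measures 0 to 0.9), the shares would be 85–86% and 89–90%.

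**Sensitivity of the share to the true ratios (variance 0.035; 18 and 21 evaluable).**

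| True ratios | Splits among failures |
|---|---|
| 1.0 / 1.0 | 88–91% |
| 0.979 / 1.0241 (Cmax ratios in 331-102-00019) | 92–95% |
| 0.95 / 0.95 | 76–80% |
| 0.90 / 0.90 | 55–59% |

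The share is highest when the ratios are near 1 or lie on opposite sides of it. It falls when both ways of taking the ODT shift together.

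**Does the first exclusion case settle a split?** No. At ratio 1.0 both Cmax point estimates lie within 0.8 to 1.25 in more than 99% of splits.

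**What an add-on would do after a split.** In the combined analysis with 12 added (balanced over three sequences), both comparisons pass in about 96% of cases at ratio 1.0, 85% at 0.95/0.95 and 60% at 0.90/0.90. These figures assume common period effects and a minimum-size add-on; 7.7 foresees estimating the size from the initial results.

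**What the text supports after a split.** Read pair by pair, 7.4 gives one positive and one negative verdict. Since 2.2.1 says both comparisons are called for, the single objective is then not met. Read jointly, one interval outside the limits is a failure. Both readings reach the same conclusion about the product.

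**The case for a change.** The strongest case for a change is that 2.2.1 justifies the arms without stating a success criterion, and that a pairwise verdict settles neither the overall conclusion nor the add-on trigger. One sentence before data lock would remove a choice otherwise made with the results in view, and that choice can decide the outcome.

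Part of this stands. No sentence addresses a split by name, the arithmetic is right under the plan's assumptions, and the first exclusion case does not help. But declaring the product equivalent on one passing comparison cannot be squared with 2.2.1. What stays open is whether to run an add-on, and 7.7 leaves that to the sponsor in any case: it says one can be performed, subject to a judgement of feasibility. Writing in the trigger would leave that discretion in place. If an add-on is run, the assessment of the combined data is already fixed in 7.4.

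The figures also need their conditions. Nine in ten is a share of failures, and failures occur in 5.8% of trials at 21 evaluable. Failure is also the case in which a true ratio of 1.0 is most doubtful, and the share and the add-on success rate both drop when the two ratios shift together.

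**Conclusion.** No change follows. This is a gap that analysts would fill sensibly: report each comparison, and claim equivalence for the ODT only if both pass. The model, intervals and limits are prespecified for each comparison, and neither reading of 7.4 alters an estimate or an interval.

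The unaddressed case has a probability of about 10% with 18 evaluable subjects and 5% with 21, assuming ratio 1.0, variance 0.035, complete data and Cmax as the limiting measure. Section 7.1 needs no correction: its 90% holds per comparison at 18 (93.7%). Power for both is 88.7% at 18, just under 90%, and 94.2% at the enrolled 21. A sentence on splits would be tidy, but it would record the reading that 2.2.1 already supports.

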7.5 Analysis of Demographic and Baseline Characteristics

For age, height, weight (screening period), BMI, and medical history and current symptoms, the frequency distribution or descriptive statistics will be presented overall and by sequence for the bioequivalence analysis set and safety analysis set.

7.6 Safety Analysis

Safety analysis will be conducted upon the safety analysis set for each formulation and administration method. Baseline is defined as the last measurement immediately before each dosing.

7.6.1 Adverse Events

Medical Dictionary for Regulatory Activities (MedDRA) will be used to code AEs. The incidence of the following events will be summarized by system organ class and preferred term.

- TEAEs
- TEAEs by severity

- TEAEs with an outcome of death
- Serious TEAEs
- TEAEs leading to discontinuation of the IMP

TEAEs potentially causally related to the IMP will also be summarized in the same way.

7.6.2 Clinical Laboratory Data

For each clinical laboratory parameter except for qualitative urinalysis, the descriptive statistics of measured values and of changes from baseline will be calculated by time point. For qualitative parameters of clinical laboratory urinalysis, shift tables versus baseline at each time point will be produced. For the clinical laboratory parameters except for qualitative urinalysis, measured values will be classified as Within Reference Range, Lower Than Reference Range, and More Than Reference Range, using the reference range of the trial site, and shift tables versus baseline at each time point will be produced.

7.6.3 Physical Examination and Vital Signs Data

For physical examination, listing of physical findings will be presented by each subject.

For each vital sign, the descriptive statistics of measured values and of changes from baseline will be presented by time point.

7.6.4 Electrocardiogram Data

For each 12-lead ECG parameter, the descriptive statistics of measured values and of changes from baseline will be calculated by time point. For 12-lead ECG assessment of normality/abnormality, shift tables versus baseline at each time point will be produced. For QTcF and QTcB, categorical analysis of measured values and of changes from baseline at each time point will be performed to calculate the number and percentage of subjects.

7.6.5 Other Safety Data

7.6.5.1 Body Weight

For body weight, the descriptive statistics of measured values and of changes from baseline will be presented.

7.6.5.2 The Columbia-Suicide Severity Rating Scale

C-SSRS data for individual subjects will be listed.

7.7 Judgement for Conduct of Add-on Subject Study

If bioequivalence cannot be demonstrated in the initial study because of an insufficient number of subjects, an add-on subject study can be performed in accordance with this protocol.

The add-on subject study will be performed using not less than half the number of subjects in the initial study. No add-on subject study will be performed in the following cases:

- 1) If the results of the initial study show that the point estimates of the geometric mean ratios for AUC_t and C_{max} between ODT and conventional tablet do not fall within the range of 0.8 to 1.25, and
- 2) If the required number of subjects for the add-on subject study estimated from the results of the initial study is considered to be a sample size that is ethically or scientifically infeasible.

7.8 Pharmacodynamic Analysis

No pharmacodynamic-related analyses are scheduled for this trial.

8 Management of Investigational Medicinal Product

2-mg brexpiprazole ODT is the test formulation provided as the IMP, and 2-mg brexpiprazole conventional tablet is provided as the reference product.

For the detailed management of the IMP and reference product, see the investigator's brochure and clinical operation manual.

8.1 Packaging and Labeling

The IMP and reference product will be provided to the IMP manager by the sponsor or designated agent. The IMP will be provided in bottles. Each IMP bottle used will be labeled to clearly disclose the statement "For clinical trial use only," as well as the trial number, IMP name, amount, lot number, expiry date, storage, and sponsor's name and address. The reference product will be provided in commercial product packaging.

8.2 Storage

The IMP and reference product will be stored in a securely locked cabinet or enclosure. Access will be limited to the IMP manager. The IMP manager may not provide IMP or reference product to any subject not participating in this protocol.

The IMP and reference product will be stored at room temperature.

The trial site staff will maintain a temperature log in the drug storage area recording the temperature at least once each working day.

8.3 Accountability

The IMP manager must maintain an inventory record of IMP and reference product received, dispensed, administered, and returned.

8.4 Returns and Destruction

Upon completion or termination of the trial, all containers of used IMP and reference product, and all unused and partially used IMP and reference product must be returned to the sponsor or a designated agent.

All IMP and reference products returned to the sponsor must be accompanied by the appropriate documentation and be clearly identified by protocol number with trial site number on the outermost shipping container. Returned supplies of IMP and reference product should be in the original containers. The assigned trial monitor will facilitate the return of containers of used IMP and reference product, and unused or partially used IMP and reference product.

8.5 Reporting of Product Quality Complaints

A Product Quality Complaint (PQC) is any written, electronic, or verbal communication by a healthcare professional, consumer, subject, medical representative, Competent Authority, regulatory agency, partner, affiliate, or other third party that alleges deficiencies or dissatisfaction related to identity, quality, labeling, packaging, reliability, safety, durability, tampering, counterfeiting, theft, effectiveness, or performance of an IMP, reference product, or medical device after it is released for distribution. Examples include, but are not limited to, communications involving:

- Failure/malfunction of a product to meet any of its specifications
- Incorrect or missing labeling
- Packaging issues (eg, damaged, dirty, crushed, missing product)
- Blister defects (eg, missing, empty blisters)
- Bottle defects (eg, under/over-fill, no safety seal)
- Product defects (eg, odor, chipped, broken, embossing illegible)
- Loss or theft of product

